6.5. Interim Analyses and Data Monitoring

Groups 2, 4, 5, and 6 will each have 2 sentinel subjects who will receive the first vaccination followed by a 48-hour observation period. The sentinel subjects for Groups 2 and 4 will be evaluated prior to continuing with dosing of the rest of Groups 2 and 4, followed by the sentinel subjects for Groups 5 and 6. In the absence of pre-defined criteria and after SRC and/or SMC meetings, the remainder of the cohorts can proceed to vaccination (see Section 4.2.1).

*Note: Sentinel subjects will not be included for Groups 1 and 3 because the dose is lower than the 2.0 mg/mL dose that was previously evaluated for these products.

6.6. Multicenter Considerations

Because the study will be performed at only one site, the University of Maryland Center for Vaccine Development, no multicenter considerations will be made.

6.7. Multiple Comparisons/Multiplicity

Multiplicity adjustments are not planned.

7. STUDY SUBJECTS

7.1. Subject Disposition

A subject disposition table (Table 1.3) will summarize overall and group-level disposition information. The table will provide the percentage of the initial group and overall population that participated for each visit period, along with completion of the screener, randomization, and immunizations. Furthermore, a detailed list of all study withdrawals (reasons for withdrawal and time of withdrawal) will be provided in Listing 1.3.

7.2. Protocol Deviations

All subject-specific deviations from the protocol (e.g., failure to return for follow-up visits or blood collection within the time indicated in the protocol) are to be documented, and presented as Listing 1.2 and Table 1.4. The PI or designee will be responsible for identifying and reporting all deviations, which are defined as isolated occurrences involving a procedure that did not follow the study protocol or study-specific procedure. Deviations will be reported annually in the continuing review report to the UMB IRB and/or the ORP and, if appropriate, in the final study report. Action taken in response to the deviation, and the impact of the deviation will be assessed by the PI or subinvestigator and recorded as significant or nonsignificant.

Any protocol deviation that adversely affects the safety or rights of a subject or scientific integrity of the study, the deviation will be reported immediately to the sponsor's representative, UMB IRB and/or the ORP.

8. SAFETY EVALUATION

Safety analysis will include data collected from the Safety Population. Adverse event data will be listed individually (including intervention and outcome) (Listings 1.11.1, 1.11.2, and 1.11.3) and summarized by body system and preferred terms within a body system for each treatment group. Serious and/or unexpected AEs will also be discussed on a case-by-case basis. For the tabulation of the AEs by body system, a subject will be counted only once in a given body system. For example, a subject reporting nausea and diarrhea will be reported as one subject, but the symptoms will be listed as two separate AEs within the class. Therefore the total number of AEs reported within a body system may exceed the number of subjects within the body system reporting AEs. Tables 4.1 and 4.2 will present data about which groups ever experienced adverse effects.

8.1. Safety Review Committee (SRC)

The SRC will be composed of:

- PI and/or subinvestigator
- Research monitor (RM)/Independent Safety Monitor (ISM)
- DMID Medical Monitor
- USAMMDA pharmacovigilance physician or designee

Objective pre-defined halting rules and safety evaluations will be utilized. For sentinel subjects, the SRC will evaluate safety data at 48 hours post first dose. If none of the pre-defined halting rules are observed in the sentinel subjects, vaccination of the remainder of the cohorts will proceed. Should any of the study halting rules be met, the PI will notify ORA PSSB within 24 hours. The SMC will meet to evaluate data and make a recommendation regarding the trial. The SMC recommendation will be documented and provided in writing to the ORA PSSB. The sponsor's representative will then decide to terminate, modify, or continue the conduct of the study. The ORA PSSB will communicate the final decision to the appropriate parties involved in the study (ie, PI, RM/ISM, and DMID). The PI will in turn notify the IRB as appropriate. USAMRMC RA Scientist will communicate the final decision to FDA as appropriate.

8.2. Demographic and Other Baseline Characteristics

Demographic descriptive statistics will be presented in tabular form (Table 1.5). The table will report frequencies of categorical demographic variables such as subject race, ethnicity (Hispanic or Latino / Not Hispanic or Latino), and sex, whereas mean, median, standard deviation, first quartile, third quartile, minimum, and maximum values will be reported for age. These summaries will be reported overall for all study participants and by treatment group. Subjects may choose to identify as more than one race, or refuse to identify altogether. For sex, subjects may choose to report as male, female, or intersex.

All demographics, concomitant medical conditions, concomitant medications, and vital signs will be provided on an individual basis in list form (Listing 1.4) in the Appendix.

8.3. Concomitant Illnesses and Medical Conditions

Concomitant illnesses and medical conditions will be recorded prior to the study and during each injection visit. Listing 1.5 will report the prevalence of concomitant illness treatment group, subject ID, condition start/end day, whether it is a pre-existing condition, if the participant is taking medication for it, and, if yes, and the concomitant medication number. Physical exam findings will also be listed in Listing 1.9. Table 1.6 will present a summary of subjects with pre-existing medical conditions.

8.3.1. Prior and Concomitant Medications

Concomitant medications will be recorded prior to the study and during each injection visit. Listing 1.6 will report all concomitant medication by time of use, type of medication, and subject group.

8.4. Measurements of Treatment Compliance

Subjects who are unable to follow the study requirements and arrive at study visits will be withdrawn from the study at the PI's discretion. Poor compliance with study visits would include the inability to come to a scheduled study visit within the proper window on 2 or more occasions. Compliance prevalence by treatment group at each study visit period will be included in the subject disposition table (Table 1.3), and Table 1.7 Visit Completion Rates by Treatment Group.

8.5. Adverse Events

The safety evaluation will center on the nature, frequency, and severity of adverse events (AEs) and/or serious adverse events (SAEs) associated with TDS-EP-based administration of HTNV and PUUV DNA vaccines.

ICH E6 Good Clinical Practice Guidelines define an adverse event (AE) as any untoward medical occurrence in a patient or clinical investigation subject administered a pharmaceutical product regardless of its causal relationship to the study treatment. An AE can therefore be any unfavorable and unintended sign (including an abnormal laboratory finding), symptom, or disease temporally associated with the use of medicinal (investigational) product.

An AE is considered to be any adverse change or exacerbation from a baseline condition that occurs following the initial administration of an investigational product whether or not the event is considered to be related to the investigational product. Examples of this include but are not limited to the following:

- Adverse changes including new signs and symptoms, intercurrent illness modifying the clinical course, or the worsening of a baseline condition including the increased frequency of an event or an increased intensity of a condition
- Concomitant disease with onset or increased severity after the start of study product administration

- A new pattern in a preexisting condition, occurring after the receipt of investigational product that may signal a clinically meaningful change
- Clinically significant changes in laboratory values

Adverse events will be classified by MedDRA® System Organ Class and Preferred Term, severity, and relationship to study treatment. AEs will be documented in terms of a medical diagnosis. When this is not possible, the adverse event will be documented in terms of signs and/or symptoms observed by the investigator or reported by the subject at each study visit. AEs occurring while on study will be documented appropriately regardless of relationship.

Any hospitalization will be considered a serious adverse event. Information to be collected include event description, date of onset, clinician's assessment of severity, relationship to study product (assessed only by those with the training and authority to make a diagnosis), and date of resolution/stabilization of the event. All AEs will be followed to adequate resolution or stabilization.

A complete listing of adverse events for each subject will provide details including severity, relationship to study product, onset, duration, and outcome. Laboratory results will be summarized by laboratory parameter, severity, study day, and study group. Figures 1.3 and 1.4 will present details of adverse effects, by group and visit number. Tables 2.1 to 2.3.4 present data about adverse effects.

8.5.1. Relationship to Investigational Product

The investigator must assign a relationship of each AE to the receipt of the investigational product. The investigator will use clinical judgment in conjunction with the assessment of a plausible biologic mechanism, a temporal relationship between the onset of the event in relation to receipt of the investigational product, and identification of possible alternate etiologies including underlying disease, concurrent illness or concomitant medications. The following guidelines should be used by investigators to assess the relationship of an AE to study product administration. **ONLY A PHYSICIAN CAN MAKE THIS DETERMINATION.**

- Not related: No relationship to investigational product. Applies to those events for which evidence exists that there is an alternate etiology.
- Unlikely: Likely unrelated to the investigational product. Likely to be related to factors other than the investigational product, but cannot be ruled out with certainty.
- Possible: An association between the event and the administration of investigational product cannot be ruled out. There is a reasonable temporal association, but there may also be an alternative etiology, such as the subject's clinical status or underlying factors (including other therapy).
- Probable: There is a high degree of certainty that a relationship to the investigational product exists. There is a reasonable temporal association, and the event cannot be explained by known characteristics of the subject's clinical state or factors including other therapy.
- Definite: An association exists between the receipt of investigational product and the event. An association to other factors has been ruled out.

The sponsor uses five categories of relatedness (defined above), which are to be used for this clinical trial. DMID uses only two categories of relatedness: “Not Related” and “Related”. The Sponsor’s category of “Not Related” maps to DMID category of “Not Related”, while the Sponsor’s categories of “Unlikely”, “Possible”, “Probable” and “Definite” map to the DMID category of “Related”.

8.5.2. Severity Assessment

All AEs will be assessed for severity by the investigator. Inherent in this assessment is the medical and clinical consideration of all information surrounding the event including any medical intervention required. Each event will be assigned one of the following categories: mild, moderate, or severe. Refer to the grading scale in Protocol Appendix C for further guidance in the assignment of severity. The criteria below may be used for any symptom not included in the grading scale. Any potentially life threatening/life threatening or fatal AE must be reported as an SAE.

The eCRF for AEs will reflect only the highest severity for continuous days an event occurred.

Mild	Grade 1	Does not interfere with routine activities; minimal level of discomfort
Moderate	Grade 2	Interferes with routine activities; moderate level of discomfort
Severe	Grade 3	Unable to perform routine activities; significant level of discomfort
Potentially life threatening	Grade 4	Hospitalization or ER visit for potentially life-threatening event
Fatal	Grade 5	Death

FDA guidelines for toxicity will be followed; however, if a subject is evaluated in an emergency room for nonlife threatening illness or symptoms (i.e., visits emergency department on weekend for mild problems because the physician’s office is closed), the information from that visit will be reviewed and severity of the adverse event will be assessed according to the subject’s clinical signs and symptoms.

As defined by the ICH guideline for GCP, the term “severe” is often used to describe intensity (severity) of a specific event (as in mild, moderate, or severe myocardial infarction); the event itself however, may be of relatively minor medical significance (such as severe headache). This is **not** the same as “serious”, which is based on subject/event **outcome** or **action** criteria usually associated with events that pose a threat to a subject’s life or functioning. Seriousness (not severity) serves as a guide for defining regulatory reporting obligations.

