4.4.2.1.2. Safety Results

During the performance of the TDS-IM V1.0 study, there were no significant safety concerns involving the investigational products. Overall, 30/31 (96.8%) subjects receiving at least 1 dose of HTNV DNA, PUUV DNA, or HTNV/PUUV DNA vaccines reported at least 1 AE. Of the 246 AEs reported, 96.7% were graded as mild to moderate. Seven out of 8 AEs identified as either Grade 3 or Grade 4 were considered unrelated to the study vaccine; 1 Grade 3 AE was considered unlikely to be related. There were 2 SAEs reported during this study, both involving transient Grade 4 laboratory abnormalities detected in otherwise asymptomatic individuals (hypoglycemia and hyperkalemia, respectively). Each event was evaluated and determined to be unrelated to study participation.

Seventy-six incidents of injection site pain were reported in 28/31 (90.3%) subjects, accounting for 30.9% of all AEs. The other most commonly reported AEs were headache (5.7%), injection site bruising (3.7%), muscle aches (3.3%), and fatigue (3.3%). Ninety-six/246 (39.0%) AEs were

considered related to injection, of which 87 (90.6%) were local reactions at the injection site (pain, bruising, or erythema).

4.4.2.2. A Phase I, Randomized, Observer-blind, Placebo Controlled Study to Assess the Safety, Reactogenicity, and Immunogenicity of a Venezuelan Equine Encephalitis DNA Vaccine Candidate Administered Intramuscularly or Intradermally by Electroporation to Healthy Adults (NCT01984983)

In a Phase 1, randomized, double-blind, placebo-controlled study, a DNA-based Venezuelan Equine Encephalitis vaccine, pWRG/VEE, or placebo control was administered to 41 healthy, adult subjects using either the Ichor TDS-IM V1.0 or TDS-ID EP devices ([Hannaman, et al, 2016](#)). Subjects received up to 3 administrations of the pWRG/VEEV vaccine. Subjects in the TDS-IM V1.0 groups received 0.5 mg (N = 8) or 2.0 mg (N = 9) of pWRG/VEE or a saline placebo (N = 4) in a 1.0-mL injection. Subjects in the TDS-ID groups received 0.08 mg (N = 8) or 0.3 mg (N = 8) of pWRG/VEE or a saline placebo (N = 4) in a 0.15-mL injection. Subjects were monitored for a total of 360 days.

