10.5. Severity Assessment

All AEs will be assessed for severity by the investigator. Inherent in this assessment is the medical and clinical consideration of all information surrounding the event including any medical intervention required. Each event will be assigned one of the following categories: mild, moderate, severe, potentially life threatening/life threatening, or fatal. Refer to the grading scale in [Appendix C](#) for further guidance in the assignment of severity. The criteria below may be used

for any symptom not included in the grading scale. Any potentially life threatening/life threatening, or fatal AE must be reported as an SAE.

The eCRF for AEs will reflect only the highest severity for continuous days an event occurred.

Mild	Grade 1	Does not interfere with routine activities; minimal level of discomfort
Moderate	Grade 2	Interferes with routine activities; moderate level of discomfort
Severe	Grade 3	Unable to perform routine activities; significant level of discomfort
Potentially life threatening/life threatening	Grade 4	Hospitalization or ER visit or urgent intervention indicated
Fatal	Grade 5	Death

FDA guidelines for toxicity will be followed; however, if a subject is evaluated in an emergency room for nonlife threatening illness or symptoms (ie, visits emergency department on weekend for mild problems because the physician's office is closed), the information from that visit will be reviewed and severity of the adverse event will be assessed according to the subject's clinical signs and symptoms.

As defined by the ICH guideline for GCP, the term "severe" is often used to describe intensity (severity) of a specific event (as in mild, moderate, or severe myocardial infarction); the event itself however, may be of relatively minor medical significance (such as severe headache). This is **not** the same as "serious", which is based on subject/event **outcome** or **action** criteria usually associated with events that pose a threat to a subject's life or functioning. Seriousness (not severity) serves as a guide for defining regulatory reporting obligations.

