APPENDIX C. CLINICAL AND LABORATORY TOXICITY GRADING SCALES

All toxicity grading scales are based upon *FDA Guidance for Industry: Toxicity Grading Scale for Healthy Adult and Adolescent Volunteers Enrolled in Preventative Vaccine Clinical Trials* (September 2007). The toxicity grading scale for lymphadenopathy is based upon *National Institutes of Health, Common Terminology Criteria for Adverse Events (CTCAE) Version 5.0* (November 27, 2017).

C.1 TABLES FOR CLINICAL ABNORMALITIES

Table C-1: FDA Toxicity Grading Scale – Local Injection Reactions

Local Reaction to Injectable Product	Mild (Grade 1)	Moderate (Grade 2)	Severe (Grade 3)	Potentially Life Threatening (Grade 4)
Pain	Does not interfere with activity	Repeated use of non-narcotic pain reliever > 24 hours or interferes with activity	Any use of narcotic pain reliever or prevents daily activity	Emergency room (ER) visit or hospitalization
Tenderness	Mild discomfort to touch	Discomfort with movement	Significant discomfort at rest	ER visit or hospitalization
Bruising	Barely perceptible difference compared to surrounding skin	Clearly discernable difference compared to surrounding skin	Unsightly difference when compared to surrounding skin	Not applicable
Erythema/Redness ^a	2.5-5 cm	5.1-10 cm	> 10 cm	Necrosis or exfoliative dermatitis
Induration/Swelling ^b	2.5-5 cm and does not interfere with activity	5.1-10 cm or interferes with activity	> 10 cm or prevents daily activity	Necrosis

^a In addition to grading the measured local reaction at the greatest single diameter, the measurement should be recorded as a continuous variable.

^b Induration/Swelling should be evaluated and graded using the functional scale as well as the actual measurement.

Table C-2: FDA Toxicity Grading Scale – Vital Sign Abnormalities

Vital Signs ^a	Mild (Grade 1)	Moderate (Grade 2)	Severe (Grade 3)	Potentially Life Threatening (Grade 4)
Fever (°C) ^b (°F) ^b	38.0-38.4 100.4-101.1	38.5-38.9 101.2-102.0	39.0-40 102.1-104	> 40 > 104
Tachycardia – beats per minute	101-115	116-130	> 130	ER visit or hospitalization for arrhythmia

Vital Signs ^a	Mild (Grade 1)	Moderate (Grade 2)	Severe (Grade 3)	Potentially Life Threatening (Grade 4)
Bradycardia – beats per minute ^c	50-54	45-49	< 45	ER visit or hospitalization for arrhythmia
Hypertension (systolic) – mm Hg	141-150	151-155	> 155	ER visit or hospitalization for malignant hypertension

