# expected scheduled visits						
# total scheduled visits						
# missed visits						
% scheduled visits completed						

TABLE 2.1: Injection Pain, Efficiency, and Speed by Treatment Group

^aIf more than one syringe was used, data from the last syringe is included in this table.

Q1: first quartile; Q3: third quartile.

TABLE 2.2: Global Summary of Adverse Events

Number of Participants Immunized= N	Possibly, Probably or Definitely Related Adverse Events	
	All Adverse Events	Events
Subjects with at least one solicited AE by 16 days of immunization [n (%)]	x (xx)	x (xx)
Total # solicited AEs [n (maximum severity grade)]	x (Grade X)	x (Grade X)
Subjects with a solicited Grade 3 AE [n (%)]	x (xx)	x (xx)
Subjects with at least one solicited local AE	x (xx)	x (xx)
Total # local AEs	x (Grade X)	x (Grade X)
Average # local AEs/volunteers experiencing local AEs	x.xx	x.xx
Subjects with at least one solicited systemic AE	x (xx)	x (xx)
Total # systemic AEs	x (Grade X)	x (Grade X)
Average # systemic AEs/volunteers experiencing systemic AEs	x.xx	x.xx
Subjects with at least one unsolicited AE within 32 days of immunization [n (%)]	x (xx)	x (xx)
Total # unsolicited AEs within 32 days of immunization [n (maximum severity grade)]	x (Grade X)	x (Grade X)
Subjects with an unsolicited Grade 3 AE [n (%)]	x (xx)	x (xx)
Subjects experiencing an SAE ^a [n (%)]	x (xx)	x (xx)
Total # of SAEs [n (maximum severity grade)]	x (Grade X)	x (Grade X)

a) An adverse event or suspected adverse reaction is considered “serious” (SAE) if, in the view of either the investigator or sponsor, it results in any of the following outcomes:

- Death
- Life-threatening adverse event
- Inpatient hospitalization or prolongation of existing hospitalization
- Persistent or significant incapacity or substantial disruption of the ability to conduct normal life functions
- Congenital anomaly/birth defect

TABLE 2.3.1: Number and Percentage of Subjects Experiencing Solicited Events by Symptom, Relationship to Study Product, and Treatment Group

NOTE: Table will be repeated for each injection dose

Symptom	Relationship to Study Product	Group 1 (N=X)		Group 2 (N=X)		Group 3 (N=X)		Group 4 (N=X)		Group 5 (N=X)		Group 6 (N=X)	
		n	%	n	%	n	%	n	%	n	%	n	%
Any Symptom	Related												
	Unrelated												
Redness, swelling, bruising, or pain (to include tenderness) at the injection site	Related												
	Unrelated												
Fever	Related												
	Unrelated												
Myalgia	Related												

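### SAP 8.5.2 contradicts its own grade table and Protocol 10.5 on severity categories, and the by-grade tables have no Grade 4 or 5 rows, so such events are merged into Grade 3 or get no grade row

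*SAP*

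**What the plan says.** SAP 8.5.2 gives the rule for severity: "Each event will be assigned one of the following categories: mild, moderate, or severe". It then points elsewhere for detail: "Refer to the grading scale in Protocol Appendix C for further guidance in the assignment of severity". The grade table printed below that sentence has five rows. Its Grade 4 row reads "Hospitalization or ER visit for potentially life-threatening event", and its Grade 5 row is death. The section also requires every life-threatening or fatal event to be reported as an SAE.

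Protocol 10.5 has the matching sentence with a longer list: "Each event will be assigned one of the following categories: mild, moderate, severe, potentially life threatening/life threatening, or fatal". Protocol Appendix C has a Grade 4 column in its local-reaction, vital-sign, systemic and laboratory tables.

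The shells in SAP Appendix I follow the shorter list:

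- Table 2.3.2 (solicited events by maximum severity and group) has rows *None*, 1, 2, 3 and *Any*.
- Table 2.3.3 (unexpected events judged possibly, probably or definitely related) has rows 1, 2, 3 and *Any*. Table 2.3.4 uses the same format.
- Table 2.2 (global summary) has the row "Subjects with a solicited Grade 3 AE [n" (%)] and a matching row for unsolicited events. Neither says 'or higher'.

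Severity of adverse events is part of the primary endpoint in Protocol 6.1 and SAP 3.3.

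**The concern.** A programmer who follows the SAP has two incompatible instructions within one section, and the table shells match only one of them. Under either instruction, the by-group tables that describe severity cannot show how many subjects had a Grade 4 or 5 event. Two analysts could each follow the SAP and produce different Grade 3 counts from the same data. With about 12 subjects per group, one subject placed differently is a visible change in a percentage.

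**Working it through.** The plan states no figure on this point, so there is none to reproduce. The check compares the passages and then fills in the shells.

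**Inputs.** Severity categories: three in the SAP 8.5.2 sentence; five in the SAP 8.5.2 table and in Protocol 10.5. Grade rows: 1 to 3 in Tables 2.3.2 to 2.3.4. Group sizes: 12 in Groups 1 to 5 and 22 in Group 6 (Protocol 6.3.1).

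**Can a solicited event reach Grade 4?** Yes. Appendix C defines Grade 4 for pain, tenderness, redness, swelling, fever, respiratory rate, headache, fatigue and myalgia. It has no Grade 4 for bruising, and its lymphadenopathy scale stops at Grade 2. The lymphadenopathy row therefore loses nothing. Bruising shares one row of Table 2.3.2 with pain, tenderness, redness and swelling, so that row can contain a Grade 4 event.

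**Two readings.**

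- Reading A: the three-category sentence governs. A Grade 4 or 5 event is labelled severe and counted in the Grade 3 row.
- Reading B: the five-grade table or Appendix C governs. The event keeps its grade, and no grade row exists for it.

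**Invented group of 12**, with maximum grades None 6, Grade 1 three, Grade 2 one, Grade 3 one, Grade 4 one:

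| | Reading A | Reading B | With rows 4 and 5 |
|---|---|---|---|
| Grade 3 row | 2/12 = 16.7% | 1/12 = 8.3% | 1/12 = 8.3% |
| Grade 4 row | none exists | none exists | 1/12 = 8.3% |
| None + grade rows | 6+3+1+2 = 12 | 6+3+1+1 = 11 | 6+3+1+1+1+0 = 12 |
| *Any* | 6 | 6 | 6 |
| Grade 3 or higher | cannot be split | not shown | 2/12 = 16.7% |

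**Size of one subject.** 1/12 = 8.3 percentage points in a group of 12; 1/22 = 4.5 points in Group 6. Under Reading B, a group whose only severe case is Grade 4 shows 0/12 in the Grade 3 row, while a group with one Grade 3 case shows 1/12.

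**What depends on grade.** SAP Tables 4.1 and 4.2 test whether a subject ever had a solicited or an unsolicited event, and Table 4.3 tests seroconversion. Protocol 11.1.1 compares event totals by body system. None of these uses grade, and SAP section 5 calls all analyses exploratory.

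**The case against.** The strongest reply is that these events are still reported. They are in the *Any* rows. Table 2.2 has maximum-grade fields with no cap at 3, and SAE rows that should capture every life-threatening or fatal event under the SAP 8.5.2 reporting rule. Listings 1.11.1 to 1.11.3 carry a severity grade column, and SAP 8 promises case-by-case discussion of serious events. SAP 8.5 also summarises laboratory results by severity and group, with no stated cap.

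This stands as far as it goes: the events do not leave the safety report. It does not supply the missing counts. *Any* carries no grade. A maximum grade is one value, not a number of subjects. The Table 2.2 shell has no group columns. Under Reading B, *Any* minus rows 1 to 3 of Table 2.3.2 recovers a combined Grade 4 or 5 count, but the reader has to do the subtraction and it cannot separate the two grades. Under Reading A nothing can be recovered from that table. Table 2.3.3 is not stated to use maximum severity, so subtraction there may not work.

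Three stronger readings are tempting, and the documents do not support them.

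- A reader might infer that the SAP caps severity at Grade 3 and that the worst events vanish. Section 8.5.2 contradicts itself; it does not set a cap. Loss from the grade rows occurs only under Reading B.
- A reader might infer that the Table 2.2 wording makes one group look safer than another. As drafted, that table is not split by group.
- A reader might project a count from the earlier Phase 1 study: "There were 2 SAEs reported during this study, both involving transient Grade 4 laboratory abnormalities". If these were two different subjects of 31, the rate is 2/31 = 6.5% (exact 95% CI 0.8% to 21.4%), and 82 × 2/31 = 5.3. That projection should not be used. Both events were laboratory abnormalities judged unrelated to participation, and neither is a solicited event here, so neither could enter Table 2.3.2. One was hyperkalemia, and potassium is not in this trial's laboratory panel. The other was hypoglycemia.

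**Conclusion.** The point holds as an inconsistency with a definite effect on the tables. The SAP 8.5.2 sentence conflicts with its own table and with Protocol 10.5. As the shells stand, any Grade 4 or 5 event is either indistinguishable from Grade 3 or absent from the grade rows, and no by-group table reports such counts directly. The effect is 8.3 percentage points per affected subject in a group of 12 and 4.5 in Group 6, assuming every enrolled subject is vaccinated and counted in the denominator. How many subjects would be affected cannot be estimated from the documents, and it may be none. The contradiction does not depend on that number. No planned test, sample size or error rate changes. It should be corrected because severity is part of the primary endpoint and the rule is wrong as written.

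**What to change.** 1. In SAP 8.5.2, replace the three-category list with that of Protocol 10.5: "mild, moderate, severe, potentially life threatening/life threatening, or fatal".
2. Add Grade 4 and Grade 5 rows to Tables 2.3.2 to 2.3.4, wherever Appendix C or the five-grade table defines the grade. The lymphadenopathy row can stay as it is.
3. In Table 2.2, change both Grade 3 rows to Grade 3 or higher.

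The cost is one sentence, two row labels and some extra shell rows. No new data are needed. Protocol section 11 has the SAP finalized before database lock, so the edit fits the existing process. The table shells carry their own version label (2.0, against 4.0 for the SAP body), so both parts need to be reissued together.
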